They will then be given their assigned product to use four times daily for two weeks. Subjects will maintain a daily diary (Appendix E) of their product usage and any oral effects they experience and will answer all diary questions. Compliance will be assessed by subject diary and measurement of when unused portion is returned to the clinic.

The subjects will be instructed not to use any other xerostomia products for the duration of the study and to follow their normal oral hygiene procedures. All subjects will be provided with a soft toothbrush and regular fluoride toothpaste to use during the study. Subjects will be scheduled to return in approximately 2 weeks, and will be instructed to refrain from eating and drinking for approximately 1 hour prior to their next visit. They will be advised to follow the instructions carefully and return to the study center with their assigned mouthrinse, and diary after 2 weeks for their next examination. Subjects will receive a reminder call prior to Visit 2.

Visit 2

After 2 weeks, subjects will return to the office to return their diary. This visit will last approximately 1.5 hour. The following will happen at this visit: The study staff will update of medical history and concurrent medications. Adverse experiences will be noted and recorded during the study.

The study examiner will perform ROAG(Appendix D) to assess the subject's oral health condition.

Subjects will complete VAS question (Appendix A), Xerostomia questionnaire (Appendix B) and OHIP-14 (Appendix C) for after 2 weeks use of the first product. At Visit 2, they will also complete Product Performance and Attributes Questionnaire for the first product (Appendix F).

A qualified dental examiner will perform OST, unstimulated saliva flow measurement and the objective measurement of xerostomia symptoms (Appendix D). Some intraoral photographs will be taken.

Subjects will then remain in the study center for 60 minutes to evaluate whether their mouth feels moist or lubricated, xerostomia relief by questionnaire at 5, 15, 30, 45 and 60 minutes after the in-office use of their assigned product rinse (Appendix G).

Visit 3

After a 1-week washout, subjects will return to the office to begin the second period of the study, using the same study procedures and be assigned the alternate treatment rinse as in Visit 1.

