At the end of Visit 4 (examination for the second product) they will go through a 1 week wash out period and then return for Visit 5 (baseline for the third product) and study will be completed in visit 6.

12.2 Describe what data will be collected.

NOTE: For studies with multiple data collection points or long-term follow up, consider the addition of a schedule or table in your response.

Response: The various data collection points are shown in Table 1 (Study Schedule).

Events	Screening	Visit 1	Visit 2	Visit 3	Visit 4	Visit 5	Visit 6
		First product		Second product		Third product	
Informed Consent, Demographics, Inclusion/Exclusion Criteria, Medical History, Concurrent meds	X						
Demographics Questionnaire	X						
Oral Soft/Hard Tissue Exam & Photos		X	X	X	X	X	X
Update of Inclusion/Exclusion Criteria, Medical History and Conmeds		X	X	X	X	X	X
Unstimulated saliva flow	X (<0.2)	X	X	X	X	X	X
VAS	X (>=4)	X	X	X	X	X	X
Questionnaires (Xerostomia, QoL)		X	X	X	X	X	X
Objective xerostomia endpoint (ROAG)		X	X	X	X	X	X
Product Distribution		X	X	X	X	X	X
Diary Disbursement		X		X		X	
Compliance Check			X		X		X
Product Attribute Questionnaire			X		X		X
Immediate Post-Rinse Evaluation			X		X		X
Adverse Events			X	X	X	X	X

12.3 List any instruments or measurement tools used to collect data (e.g. questionnaire, interview guide, validated instrument, data collection form).

Include copies of these documents with your submission.

Response:

- a. Demographics Questionnaire
- b. Intraoral camera
- c. Medical History
- d. VAS question (Appendix A),
- e. Xerostomia questionnaire (Appendix B)
- f. Oral Health Impact Profile -14 (OHIP-14) (Appendix C)
- g. Revised Oral Assessment Guide (ROAG) (Appendix D)
- h. Daily Diary (Appendix E)
- i. Product Performance and Attributes Questionnaire for the first product (Appendix F)
- j. Immediate Post-Rinse Evaluation (Appendix G)
- k. Oral soft and hard tissue examination form
- l. *Unstimulated saliva flow measurement form*
- m. *Adverse Events form*

12.4 Describe any source records that will be used to collect data about subjects (e.g. school records, electronic medical records).

Response: No source records will be used to collect data about subjects.

12.5 Indicate whether or not **individual** subject results, such as results of investigational diagnostic tests, genetic tests, or incidental findings will be shared with subjects or others (e.g., the subject's primary care physician) and if so, describe how these will be shared.

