19.0 Data Management and Analysis*

19.1 *Describe the data analysis plan, including any statistical procedures. This section applies to both quantitative and qualitative analysis.*

Response: This is a randomized double-blind placebo controlled crossover study comparing the HYDRAL Oral rinse to Biotene rinse, and HYDRAL Oral rinse to placebo. A one-week wash-out period will be adopted between phases to eliminate any possible carry-over effect of a treatment from previous phase. The primary endpoint is a reduction of dry mouth symptom in VAS (0-10 scale). To control for the Type I error rate of incorrectly rejecting the null hypothesis, a two-sided significance level of 0.025 will be used. A power analysis for a crossover study estimated that with 80% power, 33 subjects will be required to detect a minimal difference in mean VAS of 0.8. To account for withdrawal and other factors (e.g. failed measurement), a total of 39 subjects will be recruited and randomized into the study.

Descriptive statistics for all subjects will be performed for background and demographic variables. Continuous variables are expressed as frequencies (n), mean +/- SD and categorical variables are expressed as frequencies (n) and percentages (%). To evaluate the primary end point, an Analysis of variance will be applied to examine the possible residual or carryover effects of treatments. If no residual effect is found, paired t test or Wilcoxon sign-rank test where appropriate, will be used to compare treatments; however, if residual effect is significant, a mixed model (with unstructured covariance matrix) will be performed with treatment, period,

and interaction of treatment and period as fixed effects to account for treatment, period, and carryover effect. For categorical variables, percent or proportion of subjects will be calculated and a Chi-square test or McNemar test will be used. All statistical tests will be conducted using SAS version 9 (SAS Institute Inc. Cary, NC).

19.2 *If applicable, provide a power analysis.*

NOTE: This may not apply to certain types of studies, including chart/records reviews, survey studies, or observational studies. This question is asked to elicit whether the investigator has an adequate sample size to achieve the study objectives and justify a conclusion.

Response: The number of subjects needed for this study with adequate power is based on a power analysis of 0.8.

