Principal Investigator as to whether they were likely caused by the study mouthrinse and classified on the Adverse Events Form as related or unrelated to the study product. Adverse Events will also be classified as mild, moderate, or severe and reported by organ system.

21.3 Describe any safety endpoints.

Response: Adverse oral mucosal reactions.

21.4 Describe how the safety information will be collected (e.g., with case report forms, at study visits, by telephone calls with participants).

Response: Adverse events will be evaluated by the Principal Investigator as to whether they were likely caused by the study mouthrinse and classified on the Adverse Events Form as related or unrelated to the study product. Adverse Events will also be classified as mild, moderate, or severe and reported by organ system

21.5 Describe the frequency of safety data collection.

Response: At each study visit, the subject will be asked an open-ended question about whether he/she experienced any changes in general health or medication intake since the prior visit; the response will be recorded.

21.6 Describe who will review the safety data.

Response: PI

21.7 Describe the frequency or periodicity of review of cumulative safety data.

Response: At each study visit, the subject will be asked an open-ended question about whether he/she experienced any changes in general health or medication intake since the prior visit; the response will be recorded.

21.8 Describe the statistical tests for analyzing the safety data to determine whether harm is occurring.

Response: Safety will be assessed by subjective comments and oral hard and soft tissue exams. A comparison between test and placebo groups using a *t test* will allow us to compare any adverse effects occurring in the study.

21.9 Describe any conditions that trigger an immediate suspension of the research.

Response: No adverse reactions resulting in suspension of the research is anticipated. The products being tested are commercially available and have a 510(K) approval by FDA. However, if an adverse event occurs that the PI determines to (1) have a serious effect on the health and well-being of the subject

and/or (2) be treatment-related, the study will be suspended immediately and reported to the IRB as soon as possible. If the adverse event is determined to be treatment related, the study will not be resumed. without the approval of the IRB.

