23.0 Risks to Subjects*

23.1 *List the reasonably foreseeable risks, discomforts, hazards, or inconveniences to the subjects related to their participation in the research. Consider physical, psychological, social, legal, and economic risks. Include a description of the probability, magnitude, duration, and reversibility of the risks.*

NOTE: Breach of confidentiality is always a risk for identifiable subject data.

Response: Possible adverse effects include dislike for taste and allergy to ingredient(s). Subject should not be or become pregnant while on this research study. Since the ingredients are considered to be safe (GRAS) by the U.S. Food and Drug Administration and some are found in food, the risk of a bad reaction or effect is low. Increase in plaque is not anticipated since the subjects will be allowed to brush in the study using their usual brushing method. Patient's proper oral hygiene regimen should control any significant plaque accumulation.

23.2 *Describe procedures performed to lessen the probability or magnitude of risks, including procedures being performed to monitor subjects for safety.*

Response: Subjects who experience complications and discontinue the study on their own will be scheduled, if they consent, for an immediate follow-up/close-out examination to determine whether an adverse event is present, and if so, the causation of the adverse event will be recorded. If treatment is needed for any adverse event causing withdrawal, the subject will be monitored until return to normal conditions. (Every effort will be made to follow up with subjects who withdraw from the study.)

23.3 *If applicable, indicate **which procedures** may have risks to the subjects that are currently unforeseeable.*

Response: Adverse effects to the mouthrinse.

23.4 *If applicable, indicate which research procedures may have risks to an embryo or fetus should the subject be or become pregnant.*

Response: This study will not include pregnant women.

23.5 *If applicable, describe risks to others who are not subjects.*

Response: We do not anticipate any risks to non-subject individuals.

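### Section 21.8 plans a t test between test and placebo groups for adverse effects, although each subject is planned to use every rinse and the safety outcomes defined in the text are events or categories

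*Combined protocol and SAP*

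**What the plan says.** **Test.** Section 21.8 bases safety on subjective comments and tissue examinations, then states: "A comparison between test and placebo groups using a *t test* will allow us to compare any adverse effects occurring in the study". It does not say whether the t test is paired, which variable it uses, or whether the test group means HYDRAL alone or also Biotene.

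**Design.** Under section 12.1, subjects return after a washout for Visit 3 to "be assigned the alternate treatment rinse as in Visit 1". After Visit 4 "they will go through a 1 week wash out period and then return for Visit 5 (baseline for the third product". Each subject is therefore planned to use all three rinses.

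**Outcomes.** Section 21.3 names one safety endpoint: "Adverse oral mucosal reactions". Sections 21.2 and 21.4 have the investigator judge each event as related or unrelated, and add: "Adverse Events will also be classified as mild, moderate, or severe and reported by organ system". No numeric safety score is defined in the text.

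**General analysis rules.** In section 19.1 the primary comparison is explicitly within subject: "paired t test or Wilcoxon sign-rank test where appropriate, will be used to compare treatments". For categories the rule is: "For categorical variables, percent or proportion of subjects will be calculated and a Chi-square test or McNemar test will be used".

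**Expected frequency.** Section 23.1 says that "the risk of a bad reaction or effect is low".

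**The concern.** Safety on teeth and oral soft tissues is a stated objective (Study Summary and section 2.1). From section 21.8 a reader cannot tell which outcome, which test or which pairing will support the comparative safety statement.

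Three things do not fit. The wording describes two separate groups where there is one set of subjects. A test of means is applied to outcomes that the text defines as yes/no or ordered categories. And if reactions are as uncommon as section 23.1 expects, the test may have nothing to work on.

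Two related choices are also open. Table 1 records adverse events at Visits 3 and 5, each after a washout week, and section 21.8 does not say which rinse those count under. Section 22.3 replaces subjects who withdraw, and nothing says whether both the withdrawn subject and the replacement enter the safety denominator. If such choices are left until the data are unblinded, the results could influence them.

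**Working it through.** The plan gives no event rate, significance level, power or sample size for safety, so there is no planned figure to reproduce. From the documents: 39 randomized, 33 required by the power calculation (section 19.1), three products per subject (section 12.1). All rates and within-subject correlations below are assumptions.

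**1. Standard error if the groups are treated as independent.** With rates p1 and p0 and correlation r between a subject's two yes/no outcomes:

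- Unpaired: SE = sqrt{[p1(1−p1) + p0(1−p0)] / N}
- Paired: SE = sqrt{[p1(1−p1) + p0(1−p0) − 2r·sqrt(p1(1−p1)p0(1−p0))] / N}

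Take p1 = 0.30, p0 = 0.10, N = 39. The variances are 0.21 and 0.09, which sum to 0.30, and sqrt(0.21 × 0.09) = 0.1375.

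| r | Unpaired SE | Paired SE |
|---|---|---|
| 0 | 0.088 | 0.088 |
| 0.2 | 0.088 | 0.079 |
| 0.44 | 0.088 | sqrt[(0.30 − 0.121)/39] = 0.068 |

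Full enumeration of the paired 2×2 table at r = 0.44 gives true coverage of the nominal 95% interval of 98.6% unpaired and 94.3% paired. The unpaired interval is therefore too wide when reactions cluster within subjects. At r = 0 the two standard errors are equal.

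**2. The same effect in one table.** Suppose 12 of 39 subjects react on the test rinse and 6 on placebo, and all 6 are among the 12. The unpaired t test gives p = 0.110, exact McNemar 0.031 and paired t 0.012. The reading depends on a choice that section 21.8 does not make.

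**3. No reactions on either rinse.** Every value is then zero and the t statistic is 0/0, paired or unpaired. At r = 0 the chance is [(1−p1)(1−p0)]^N:

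- 2% and 2%, N = 39: 0.98^78 = 0.207
- 1% and 1%, N = 39: 0.99^78 = 0.457
- 5% and 1%, N = 39: (0.95 × 0.99)^39 = 0.091

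At r = 0.2 these become 24%, 49% and 11%.

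**4. What the counts still show.** With no events in n subjects, the exact two-sided 95% upper limit is 1 − 0.025^(1/n). For 0/39 this is 9.0%; for 0/33 it is 10.6%. The study could then say what reaction rate it excludes, while the planned test says nothing.

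**5. Sections 19.1 and 21.8 side by side.** Section 19.1 writes the word paired where it means a paired t test; section 21.8 does not. Section 19.1 sends categorical variables to chi-square or McNemar; section 21.8 sends adverse effects to a t test. Of the two tests in 19.1, only McNemar respects the pairing.

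**The case against.** **The t test may simply mean a paired t test.** If so, the standard-error problem in step 1 goes away. The categorical scale, the empty result when nothing occurs, and the mismatch with 19.1 remain.

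**The rule in 19.1 may not govern safety.** It is general and does not mention safety, whereas 21.8 is specific. If 19.1 does apply, it already plans percentages per category, and only the intervals would be new. This stands: a reader might infer a flat contradiction, but the documents show only a specific sentence that does not follow a general rule.

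**Some safety data may be numeric.** The tissue examination form, Adverse Events Form and daily diary are not in the text reviewed. A score or a count of days with symptoms could suit a paired t test. This stands, so the point is confined to the outcomes the text defines.

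**The assumed rates may be unrealistic.** Rates of 30% and 10% sit poorly with section 23.1, and the suspension rule in 21.9 makes many related reactions unlikely to accumulate. That case only shows the direction and size of the pairing error. Low rates make step 3 more relevant.

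**A reader might infer that t intervals are generally too narrow at low rates.** The numbers do not support this. At 5% against 1%, r = 0.2, N = 39, paired-t coverage computes as 83.4%. But 13.3 of the 16.6 missing points are tables with no discordant pair, where the paired t test is undefined. Where an interval exists, coverage is 83.4/86.7 = 96% paired and 86.3/89.1 = 97% unpaired. Of the unequal low-rate cases run (5% against 1% and 10% against 2%, each with 39 and 33 pairs), only 10% against 2% with r = 0.3 and N = 39 keeps a real shortfall, about 87% paired and 92% unpaired. It disappears at N = 33.

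**A reader might infer that McNemar gains power.** It does not. With 4 reactions against 0 in 39 subjects, paired t gives p = 0.044, unpaired t 0.041, mid-p McNemar 0.063 and exact McNemar 0.125.

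**Conclusion.** The point holds. As written, the safety test in section 21.8 does not fit a three-period crossover or the safety outcomes that the protocol text defines.

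The pairing error applies only if the test is read as independent-groups, and its size depends on how strongly reactions cluster within subjects: none at correlation 0, and a standard error of 0.088 instead of 0.068 in the assumed 30% against 10% case. The empty result when nothing occurs applies on either reading, with a chance of roughly one in five to one in two if both true rates are 1% to 2%.

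Severity is minor to moderate. What is affected is the comparative safety statement. The primary endpoint, the investigator's review of individual cases and the suspension rule in 21.9 are not touched. The documents do not support a claim that the trial's safety monitoring fails, that t intervals are generally too narrow here, or that another test would detect more.

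**What to change.** Replace the t test sentence in section 21.8 with:

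> For each rinse, report the number and percent of subjects with any adverse event, any related adverse event and any adverse oral mucosal reaction while using that rinse, with exact 95% CIs, counting every subject who used the rinse, including those who withdrew or were replaced. Compare HYDRAL with placebo within subject by the paired risk difference with a 95% CI suited to small counts, with McNemar's test as support. Show Biotene the same way, descriptively. Events first reported at Visit 3 or 5 are listed under the rinse just stopped.

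If the tissue examination form or the diary yields a numeric score, name it and use the paired comparison already in 19.1. In 19.1, state that between-rinse comparisons of binary outcomes use McNemar and not chi-square.

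The choice of small-sample interval is partly preference; what matters is naming one before unblinding. The counts should lead.

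**Cost.** A few sentences in 21.8 and a clause in 19.1, with no new data. McNemar has low power with few events and is also uninformative when no pair is discordant. Paired comparisons omit subjects without both periods, although the counts per rinse keep them.

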22.0 Withdrawal of Subjects*

- N/A: This study is not enrolling subjects. This section does not apply.

22.1 Describe **anticipated** circumstances under which subjects may be withdrawn from the research without their consent.

Response: Subjects enrolled in the study may elect to withdraw at any time for any reason. Additionally, subjects may be withdrawn from the study at the request of the Principal Investigator for the following reasons:

1. Subject does not return for follow-up and cannot be contacted to reschedule within +/- 5 days of each visit.
2. An adverse event that requires discontinuation of the study mouthrinse in the judgment of the Principal Investigator
3. Subject refusal or failure to comply with the study protocol
4. Protocol violation(s) or deviation(s) that compromise the use of the subject's data
5. Subject has started taking any concomitant medications that interfere with results including anticoagulants, NSAIDS, or drugs that have been shown to enlarge gingival tissues.

22.2 Describe any procedures for orderly termination.

NOTE: Examples may include return of study drug, exit interview with clinician. Include whether additional follow up is recommended for safety reasons for physical or emotional health.

Response: All subjects withdrawn from the study by request or by the Principal Investigator must be seen, if they consent, for a close-out evaluation. The reason for withdrawal will be recorded by the Principal Investigator or designee. Subjects who experience complications and discontinue the study on their own will be scheduled, if they consent, for an immediate follow-up/close-out examination to determine whether an adverse event is present, and if so, the causation of the adverse event will be recorded. If treatment is needed for any adverse event causing withdrawal, the subject will be monitored until return to normal conditions. Every effort will be made to follow up with subjects who withdraw from the study. The unused product will be disposed

22.3 Describe procedures that will be followed when subjects withdraw from the research, including retention of already collected data, and partial withdrawal from procedures with continued data collection, as applicable.

Response: If patients withdraw or are withdrawn from the study, the reason for withdrawal will be retained and de-identified in the final report of the study. Subjects who withdraw prior to last visit will be replaced with another subject and given the same treatment. To maintain the double-blind, the treatment will be determined by a third party who provided the randomization codes.

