20.2 A. *How long will the data be stored?*

Response: The data will be stored for duration of study, data analysis and possible publication (anticipated total of 6 months).

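### The default paired test drops withdrawn subjects' recorded VAS scores from incomplete comparisons, because the mixed model that could use them runs only after significant carryover

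*Combined protocol and SAP*

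**What the plan says.** Section 19.1 sets the default primary comparison: "If no residual effect is found, paired t test or Wilcoxon sign-rank test where appropriate, will be used to compare treatments". The alternative is conditional: "if residual effect is significant, a mixed model (with unstructured covariance matrix) will be performed". The same section sizes the trial at 33 subjects and adds an allowance: "To account for withdrawal and other factors (e.g. failed measurement), a total of 39 subjects will be recruited and randomized into the study".

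Section 22.3 then replaces anyone who leaves early: "Subjects who withdraw prior to last visit will be replaced with another subject and given the same treatment".

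The primary outcome is recorded as each product is finished. For Visit 2, section 12.1 says: "Subjects will complete VAS question (Appendix A), Xerostomia questionnaire (Appendix B) and OHIP-14 (Appendix C) for after 2 weeks use of the first product". Table 1 in section 12.2 repeats the VAS at Visits 4 and 6. For subjects who leave, section 22.2 says: "All subjects withdrawn from the study by request or by the Principal Investigator must be seen, if they consent, for a close-out evaluation". It does not say whether the VAS is asked then. No section defines an analysis set or a method for missing values.

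**The concern.** With three products in three periods, a subject who leaves after one product has one usable VAS score, and a subject who leaves after two has two. A paired test keeps a subject only in comparisons where both products were scored. The mixed model already named in 19.1 can use partial sequences, but whether it runs depends on a carryover test, which has nothing to do with who withdrew.

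If subjects tend to leave after a poor score on one product, the pairs that remain flatter that product. If they leave for unrelated reasons, only precision is lost. Adding new subjects restores the number of pairs, but those pairs pass through the same filter.

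**Working it through.** **Inputs from the documents.** Section 19.1: difference 0.8, two-sided level 0.025, power 80%, 33 subjects raised to 39. Section 12: three products, VAS after each.

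**Assumptions, not in the documents.** SD of paired differences 1.43; between-subject SD 1.0 to 2.0; 3 or 6 of 39 leave; six sequences used equally; no period effect. For the bias figures there is no true difference, and the tendency to leave has correlation 0.5 with the VAS just recorded (1.0 as an upper bound).

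**Step 1: the plan's own figure.** No SD is stated, so 33 can only be solved backwards. The normal formula n = [SD × (2.241 + 0.842) / 0.8]² with n = 33 gives SD = 0.8 × √33 / 3.083 = 1.49. The exact noncentral t gives 1.43. With 1.43, power is 80.1% at 33 pairs, 81.5% at 34 and 87.2% at 39. The 39 fits 33 / (1 − 0.15) = 38.8, but no withdrawal rate is stated.

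**Step 2: shift in the paired comparison, all exits after a recorded HYDRAL VAS, 6 leaving.**

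- Within-subject variance: 1.43² / 2 = 1.022. SD of one VAS: √(1 + 1.022) = 1.42 for between-subject SD 1, and √(4 + 1.022) = 2.24 for SD 2.
- HYDRAL falls in period 1 or 2 in four of six sequences, so 26 of 39 can leave after it with something still to come. The leaving fraction is p = 6/26 = 0.231, the normal cut-off 0.736 and its density 0.304, so λ = 0.304 / 0.769 = 0.396.
- Among those of the 26 who stay, the HYDRAL score is too low (too good) by ρ × 1.022 / SD × λ. This is 0.5 × 1.022 / 1.42 × 0.396 = 0.142 (SD 1) or 0.5 × 1.022 / 2.24 × 0.396 = 0.090 (SD 2).
- Largest case, completers only, SD 1: 20 of the 33 completers come from this group, so 0.142 × 20/33 = 0.086.
- Smallest case, all available HYDRAL-placebo pairs, SD 2: leavers who had already finished placebo (about a quarter) keep their pair, leaving 39 − 6 + 1.5 = 34.5 pairs. Of these, 19.5 × 0.769 = 15 are selected, so 0.090 × 15/34.5 = 0.039.

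Simulation gives the same range, 0.039 to 0.086. With 3 leaving it is 0.02 to 0.05. At correlation 1 with 6 leaving it is 0.08 to 0.17.

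**Step 3: exits not all after HYDRAL (6 leaving, correlation 0.5).** With half after HYDRAL and the rest split evenly, the HYDRAL-placebo shift is about 0.00 to 0.02. With equal exits it is below 0.01. With all exits after placebo it is the Step 2 size, against HYDRAL.

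**Step 4: mixed model against pairs (39 subjects, 4000 runs, random subject effect; treatment, period and sequence fixed).**

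| Setting, 6 leaving | Paired shift | Mixed-model shift |
|---|---|---|
| After a recorded HYDRAL VAS, correlation 0.5 | 0.04–0.09 | 0.00–0.01 |
| Before the HYDRAL VAS, correlation 0.3–0.5 | 0.04–0.10 | 0.05–0.12 |

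In the first row the paired test rejects in 2.5–2.9% of trials (2.8–3.6% with replacement) against 2.5% nominal. At correlation 1 it rejects in 3.2–6.0% (3.4–7.2% with replacement), and the mixed model in 2.3–2.7%.

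**Step 5: power at 0.8.**

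| Setting | Paired | Mixed |
|---|---|---|
| No losses | 87.2% | 88.9% |
| 6 random exits, replaced | 87.9% (available pairs) | 89.7–89.9% |
| 6 random exits, not replaced | 83.0% (available pairs), 81.4% (completers) | 85.6–85.9% |

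With no losses the gain comes from error degrees of freedom, 74 against 38. A direct noncentral t calculation gives 88.3%, so the gain there is 1 to 2 points. It relies partly on equal variances across products.

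**The case against.** **The effect is small and one-sided by assumption.** This stands. Step 2 puts every exit after HYDRAL and spends the whole allowance of 6, which also has to cover failed measurements. Section 23.1 states that "the risk of a bad reaction or effect is low", and 21.9 suspends the study after a treatment-related adverse event, so a run of product-related exits in a continuing trial is unlikely.

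**The model repairs only one kind of exit.** This also stands. Adverse events, non-compliance and dislike of taste mostly act during use, before the VAS is taken. In that case the mixed model is slightly worse than pairs.

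**The power gain owes little to withdrawn subjects' data.** Largely right once replacement is counted. The gain is then 1.8 to 2.0 points, against 1.7 with no losses at all, so the partial data add about 0.1 to 0.3 points.

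**An unstructured covariance may not hold its level.** Without a small-sample correction it rejected in 3.3–3.5%, but in only 300 to 400 runs (standard error about 1 point). The corrected version was not run.

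A reader might also infer three stronger things. One is that withdrawn subjects' data are thrown away. The plan does not say so: section 20.2 A says "The data will be stored for duration of study, data analysis and possible publication", and the gap is in how the data are used. Another is that replacement biases the trial. It does not: the selection is the same with or without it. The third is that the comparison is tilted towards HYDRAL. Nothing in the documents says which product subjects would leave.

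**Conclusion.** The point holds at low severity, as a cheap improvement to section 19.1. Whether recorded VAS scores from partial sequences count depends on a carryover test unrelated to withdrawal, and by default they are lost from any incomplete comparison.

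The likely bias is a few hundredths of a VAS point: at most about 0.09 with 6 one-sided exits at correlation 0.5, which is 0.09 / 0.8 = 11% of the planned difference. It can go either way. The figures rest on the back-solved SD of 1.43 and on assumed exit patterns. They do not support calling the planned analysis invalid or the trial underpowered.

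Two matters in 22.3 are wording only. There is no maximum number randomised; replacing until 39 complete would mean about 42 (3 leaving) to 47 (6 leaving). It is also unclear whether a replacement follows the same product sequence.

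**What to change.** In section 19.1:

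- Make the primary analysis a mixed model with treatment, period and sequence as fixed effects and a random subject effect (or an unstructured covariance with a small-sample degrees-of-freedom correction), not conditional on a carryover test.
- Use every recorded after-treatment VAS from all randomised subjects, both those who withdraw and their replacements.
- State how values are handled from subjects withdrawn under reason 4 of section 22.1 (deviations that compromise their data).
- Keep the paired analysis as a sensitivity analysis, and report withdrawals by the product in use.

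In section 22.2, state whether the close-out evaluation includes the VAS and how that value is used. If it stands for the unfinished period, the shift from exits before the VAS falls to about 0.00 when all consent and 0.02 to 0.05 when half do. The benefit goes only as far as subjects consent and the value can represent the period.

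In section 22.3, state the maximum number randomised and whether a replacement takes the same sequence. Replacement can stay.

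The cost is plan wording, slightly more analysis work and, if chosen, one VAS question at an evaluation already provided for. No visits or subjects are added. The downside to state openly is that, without a close-out VAS, the model is slightly worse than pairs for subjects who leave before the product is scored.
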